**Exclusion Criteria:** Participants with any of the following pre-existing medical conditions will be excluded from the trial: **1)** neurological injury other than SCI,(e.g. cauda equina or distal conus injuries resulting in limb or sacral areflexia; **2)** Unhealed fracture in either lower or upper extremities; **3)** Severe scoliosis, hip knee range of motion (ROM)  $>$  20 degrees. or flexion knee contractures **4)** Uncontrolled hypertension (BP  $>$ 140/90 mmHg) and severe orthostatic hypotension (BP drop  $>$  20 mmHg) or inability to maintain a sitting position ; **5)** Other medical conditions like cardiovascular disease, uncontrolled type II DM, insulin-dependent DM, or symptomatic urinary tract infection; **6)** severe hypercalcemia (defined as Serum calcium  $>$ 16 ng/mL); **7)** anti-coagulant or anti-platelet therapy, including aspirin. **8)** pacemakers and/or defibrillator devices in place, metallic implants, shrapnel or bullets in the vertebral column, or other contraindications for MRI; **9)** DXA total body-score  $<$  -2.5, knee BMD scores  $<$  0.6 g/cm^2; **10)** Participants with spasticity that is severe or adjudged a contraindication by the site Physician or limited ROM will be excluded. **11)** Pressure ulcer of the trunk, pelvic area, or lower extremities of  $\geq$  stage 3; **12)** Psychopathology history that may conflict with study objectives; **13)** Potential participants who are not wheelchair users and cannot transfer with sliding boards or portable lifts.**14)** serum Vit. D  $>$  40 ng/mL; **15)** abnormal/elevated calcium level **16)** pregnancy (female participants). Medically accepted birth control is required to enter this study. This may include, but is not limited to, birth control pills, IUD's, condoms, diaphragms, implants, being surgically sterile, or being in a post-menopausal state. A blood pregnancy test will be conducted to rule out any pregnancy before the study at the McGuire VAMC. The test will be repeated every month during the course of the study. The blood samples will be sent to the McGuire VA pathology lab for analysis. **17)** Any condition that, in the judgment of the principal

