#### **WHO-Quality of Life (QOL) Survey:**

Participants will be given a survey regarding their health, wellness and QOL to determine whether exercise programs could enhance QOL after SCI. The WHO-QOL is a survey that rates six broad domains on health (physical, psychology, level of independence, social relations, environment, and spirituality/religion/personal belief), using a five-point scale (1-5) to produce a total of 100 items in the assessment. Participants will be given the survey at the beginning and at the end of the study. The survey takes about 15 minutes to complete.

**Measurements:** All training aspects and measurements will be conducted at the Central Virginia VA Health Care System (CVHCS) SCI Exercise Physiology & Body Composition Laboratory. All participants will undergo bone assessment measurements with MRI and DXA (**specific aim 1**); measurements of bone biomarkers and weekly dietary recalls (**specific aim 2**). All testing procedures will be conducted a week to training (**baseline**) and post-intervention for **Aim 1** and **baseline, 4.5 mos and 9 mos** for **Aim 2**. Will get MRI of thigh skeletal muscles to determine muscle CSA, trabecular bone parameters (including BMF), cortical porosity and CSA. To ensure consistency of dietary intake for protein, sodium, calcium, and phosphorous, team dietitian will contact participants once a month to advise on diet. Evaluation of participants will involve

cardiovascular assessments (EKG), heart and carotid auscultations, assessment of jugular venous pulse, peripheral pulses to identify any significant factors that may impact cardiovascular health, respiratory assessment (inspection, palpation, percussion, lungs auscultation, pulse oximetry and respiratory rate), and assessment of pain. Blood analysis will include: BALP, P1NP, CTX, 25-(OH)D, PTH, complete renal panel, calcium, magnesium and Hemoglobin A1c. While previous work from our institution used urinary NTX, the current standard for bone resorption test is considered to be serum CTX. These markers will be obtained fasting at baseline, 4.5 months and 9 months; and would require no more than 10ml of blood sample (each time) from study participants.

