Falls could occur during transfers with sliding board or portable lift from bed to wheelchair and from wheelchair unto intervention equipment (rowing machine). This requires careful use of equipment. To avoid this kind of accident, transfer techniques will be reviewed with participants and caregivers (where applicable) at the beginning of the study. However, this rarely occurs after a Veteran has successfully completed rehabilitation treatment post injury.

- Protection against risk of fracture

Every effort will be taken to minimize possible bone fracture; DXA scan will be performed as detailed earlier prior to enrollment in the trial. Persons with T-score less than -2.5 SD at the hip joints or with bone mineral density less than 0.6 gm/cm^2 at the knee joints will be excluded from the trial.

- Protection from autonomic dysreflexia

Blood pressure (BP) will be monitored closely during the entire intervention and established AD protocol followed should participant experience AD symptoms (patients and caregivers usually receive training on AD management at home, during their rehabilitation course). Any significant rise in BP greater than 20 mmHg above resting BP, the intervention will be suspended immediately and AD protocol instituted. The PI will remain on video connection until AD symptoms resolved and participant returns to normal state.

- **Protection against medications adverse effects**

Medication associated with the current trial can cause allergic reactions, such as, rashes, nausea, vomiting, and hypercalcemia. The PI will obtain allergy history (prior reactions) and monitor the patient and blood parameters closely during the course of the trial to avert any serious drug reaction.

**Study removal criteria may include:** Participants may be withdrawn from the study by the research team for the following concerns:

1. New medical diagnosis of carcinoma of the breast or prostate as these would may have bone health implications. Deep venous thromboembolism as this will hinder intervention and may increase risk of pulmonary embolism; stroke, hypertension, serious heart problems, heart failure, myocardial infarction, ventricular arrhythmia, exertional chest pain, insulin dependent diabetes, hypercholesterolemia, hypertriglyceridemia, impaired liver function, hypercalcemia, or significant renal dysfunction.
2. Hospitalization for acute medical problems (e.g. Liver enzymes (AST / ALT) >1.5 times normal upper limit).

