3. Serum calcium greater than 16mg/dL or symptoms of hypercalcemia
4. Severe peripheral edema, classified as 2+ or higher
5. Any SAE that the SCI physician, [name], deems necessary for withdrawal for participant's safety.

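### The removal list gives two unreconciled calcium triggers, and the two exclusion lists show the same split, so participants could be admitted or removed inconsistently

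*Combined protocol and SAP*

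**What the plan says.** The study removal criteria stand under Protection Against Risk and allow, but do not oblige, the research team to withdraw participants from the study. Item 1 opens with "New medical diagnosis of carcinoma of the breast or prostate" and runs through a series of conditions ending "impaired liver function, hypercalcemia, or significant renal dysfunction". No calcium level, severity or symptom qualifier is given there. Item 3 reads "Serum calcium greater than 16mg/dL or symptoms of hypercalcemia".

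Calcium at entry is covered twice. In Research Design and Methods, item 6 of the Exclusion Criteria bars severe hypercalcemia, defined as above 16 ng/mL, and item 15 bars any "abnormal/elevated calcium level". In the Human Subject Section, item 13 of the Exclusion criteria bars only severe hypercalcemia, above 16 mg/dL.

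The risk table and the paragraph on medication adverse effects both name hypercalcemia as a possible harm of vitamin D, which both arms take for 9 months. Calcium is scheduled at baseline, 4.5 and 9 months (Specific aim 2). The recruitment plan anticipates no attrition. The Data Analysis Plan compares arms after the intervention by ANCOVA with baseline as covariate, and does not say how missing outcomes are handled.

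**The concern.** The same laboratory result can meet one line of the removal list and fall short of another, and the text gives no order between them. It concerns a recognised harm of the study drug, so the safety action could depend on which line the team consults. Entry has the same weakness: whether a person with mildly raised calcium is eligible depends on which of the two exclusion lists is used.

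There is also a statistical cost. The list withdraws people from the study, not merely from the intervention. With 10 per arm and no allowance for loss, each removal may cost a 9-month outcome, and an unclear trigger makes it hard to explain afterwards why that outcome is missing.

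**Working it through.** No sample size, power or alpha figure bears on this point, so the check sets the criteria side by side.

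**Removal.** Item 1 is taken as written (any newly diagnosed hypercalcemia) and so is item 3.

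| Calcium during the study | Symptoms | Item 1 met? | Item 3 met? |
|---|---|---|---|
| Not raised | No | No | No |
| Raised, at or below 16 mg/dL | No | Yes | **No** |
| Raised, at or below 16 mg/dL | Yes | Yes | Yes |
| Above 16 mg/dL | Either | Yes | Yes |

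The items part in the second row. Its lower edge is the laboratory's upper limit, which the documents do not give. If item 1 applies as written, the number in item 3 adds nothing, because anyone above 16 mg/dL already meets item 1. If item 3 is meant to be the calcium rule, item 1 is broader than intended. The text does not settle which.

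**Entry.** Take a candidate with raised calcium at or below 16 mg/dL.

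- Research Design and Methods, item 15: excluded.
- Human Subject Section, item 13: not excluded by the calcium line. Only the general clause on the investigator's judgment could apply.

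**Units.** Item 6 of the first list uses ng/mL; the second list and removal item 3 use mg/dL. Since 1 mg/dL = 1,000,000 ng / 100 mL = 10,000 ng/mL, the limit of 16 mg/dL equals 160,000 ng/mL. The two printed limits differ by a factor of 160,000 / 16 = 10,000, so they cannot both be the intended definition of severe hypercalcemia.

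**Scale.** With 10 per group and 20 in total, one lost participant is 1/10 = 10% of an arm and 1/20 = 5% of the trial. The documents give no rate of hypercalcemia from which to work out an expected number of removals.

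**The case against.** The strongest reply is that the removal list is permissive and any one item is enough. Item 3 does not forbid action under item 1; the two overlap, and a clinician can use judgment. That is right as far as it goes. A reader might infer that the list is logically impossible to follow, or that participants will be removed inconsistently. The documents support neither; they support two unreconciled triggers that could lead to uneven action. Discretion does not cure this, because it does not tell the team which calcium line to start from.

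A reader might also infer that the single scheduled mid-study blood test decides everything. It does not: item 3 also acts on symptoms, and Protection Against Risk allows unscheduled safety visits and promises close monitoring of blood parameters.

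Entry and removal limits may properly differ, and items 6 and 15 of the first exclusion list are merely redundant, since 15 contains 6. Both points stand. What remains is the disagreement between the two exclusion lists, and the units.

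The risk table rates vitamin D toxicity as rare, and after the two-week lead-in both arms take the same daily dose. Few removals may therefore arise, and nothing in the documents shows that they would differ between arms. A claim of bias in the treatment comparison would go too far.

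Finally, the list names lipid and liver conditions, while the Measurements paragraph reads "Blood analysis will include: BALP, P1NP, CTX, 25-(OH)D, PTH, complete renal panel, calcium, magnesium and Hemoglobin A1c", with no liver or lipid test. It is tempting to call those grounds unworkable. They are not: item 1 is framed around new diagnoses, item 2 is "Hospitalization for acute medical problems (e.g. Liver enzymes (AST / ALT) >1.5 times normal upper limit", so the enzyme value is an example attached to hospitalization, and the Adverse Events section provides for laboratory tests and chart review. The study does not schedule these tests, so detection depends on usual care, hospital or chart results. That is a side note, not an error.

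**Conclusion.** The point holds as an unreconciled safety criterion. Removal items 1 and 3 differ for every symptom-free participant whose calcium is raised but at or below 16 mg/dL, and the two exclusion lists differ over the same range, with a unit mismatch in one of them. All 20 participants take the study drug, so all fall under the ambiguous rule. How many would be affected is unknown and may be few; the 10% of an arm is the weight of one lost participant, not a forecast.

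The conclusion assumes that hypercalcemia in item 1 carries its plain meaning of any newly diagnosed raised calcium. If the authors meant only the severe form, the wording still has to say so. No view is taken on which calcium level is clinically right.

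**What to change.** 1. The study's clinicians should reconcile removal items 1 and 3 into one stated calcium trigger for removal. They should likewise reconcile the calcium lines of the two exclusion lists into one stated trigger for entry, in one unit. The two decisions need not share a level, and none is proposed here.

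2. Separate removal from the intervention from removal from the study. Where the participant consents and it is safe, those taken off the intervention should still have the 9-month outcome assessments, and the Data Analysis Plan should say how those data are used.

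The first change costs only protocol wording. The second costs a few extra visits for participants who are off the intervention, using assessments already planned.

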**Protection against possible participants' coercion:**

The \$300 paid to each participant is to compensate for time and inconveniences associate with the commitment to participate in a 9 months trial and would be paid in 2 installments (\$150 will be disbursed at the end of the 4.5 months testing and the end of the study, respectively) to protect against coercion. Furthermore, the PI will work closely with the IRB to avoid any coercive influence on any of our study participants.

**Adverse Events:**

All participants will be monitored for any changes in health status from baseline. The SCI Provider on record for each participant will be notified of any changes that may require attention. An adverse event is any experience that has taken place during research project, which, in the opinion of the investigators, was harmful to the research participant, increased the risks of harm in the research, or had an unfavorable impact on

the risk/benefit ratio. Adverse events will be monitored throughout the study period via physical examinations, vital signs, laboratory tests, review of medical charts, and verbalized concerns by the participants, caregivers, significant other or family member. Any adverse event will be documented in each participant's file. Files will be reviewed for adverse events, protocol violations, and reasons for dropouts/withdrawals every ten days. The PI will provide CVVHCS IRB an annual summary of adverse events. All serious adverse events (SAEs), such as those that are life-threatening or involve hospitalization, will be promptly reported to CVVHC IRB Research Subjects Protection Program. Serious adverse event is defined as the unexpected medical occurrence associated with the research procedure that may lead to death, life-threatening medical condition, inpatient hospitalization for or longer than 24 hours, persistent or significant incapacity or substantial disruption of the ability to engage in normal activities of daily living.

During the study period and at the completion of the study, all participants will continue to receive their usual health care from their assigned SCI Provider and/or other Providers within and outside VHA health care system. When study procedures begin, the importance of reporting any perceived problem, adverse event or change from baseline health will be stressed to the participants. Examples of potential problems requiring immediate medical attention or a call to the PI will be described to the participants. Above all, it will be stressed to the participants that direct phone access to the PI is available 24hrs/day, 7 days a week and in the event of any questions or concerns, they are to call the PI with the phone number that they were given. All participants will be identified by an assigned number. Participants' research charts will be kept in the PIs office which is locked inside a locked file cabinet. Only the PI and Co-PI will have access to participants' study records and medical information. A master sheet of the full names will be kept in the locked file in the PI's office. All completed study files will be stored in the mentor's SCI research office 1V-129. At the end of 4-year period, all records will either be stored in the SCI Research Exercise Laboratory locked room or sent to Dunmar Storage Facility based on space needs.

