#### **Passive range of motion or passive stretching:**

Participants assigned to the passive exercise and Vitamin D group will have their caregivers perform passive ROM. Caregivers will be instructed to sit on a stool, cup the participant's leg above the ankle joint, and move it from 90-degrees of knee flexion to full knee extension. The leg will be maintained in extension for 5 sec and returned to flexion for 5 sec. The passive actions are repeated in the manner described in the RT protocol; 10 reps on the right leg followed by 10 reps on the left leg for 4 sets x 10 reps. This exercise training will take place twice a week. Each training exercise will last 30 – 40 minutes each day of the exercise.

**Blood Pressure (BP) Monitoring:** The caregiver will measure the participant's BP before starting the exercise, record the reading and leave the BP cuff in place. About 15 to 20 minutes into the exercise, another BP reading will be taken and the final reading at the end of the exercise to safeguard against Autonomic Dysreflexia (AD). Most individuals with high cervical and thoracic levels of SCI own BP machines. However, if they do not own one, they are eligible to get one from their Providers.

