**Data Analysis Plan:** IBM SPSS statistical software version 26 will be used. Being a pilot study, primary analyses will be mainly descriptive. Means and SD will be estimated for utilization (number of sessions completed), with each outcome. Finally, analysis of covariance (ANCOVA) will be used to test differences between groups post intervention for each outcome, using the baseline score as a covariate. If normality of groups appears to be violated in the sample normalizing transformations or non-parametric statistics will be considered.

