## **Risk to Subjects.**

Every effort will be made to minimize potential harm to individuals during the study. There will strict adherence to the protocol's inclusion/exclusion criteria. However, the following may pose potential risk to study participants:

Potential source of risk	Potential Risk	Possibility of occurring
Pressure to skin from weights or skin irritation from weights or during exercise	Pressure injury (break to skin)	Occasionally but no more than usual from daily activities
DXA/MRI	No significant risk This research study will involve exposure to radiation from 2 whole body DEXA scans and MRI with no contrast. This radiation exposure is not necessary for medical care and is for research purposes only. All radiation exposure increases the risk of developing cancer in the future. The total amount of radiation that would be used in this study is equal to less than one day of exposure from natural background radiation. Permission would be obtained from the CVVHCS Radiation Safety Committee, who will review the use of radiation in this research study, involving minimal risk and necessary to obtain the desired research information. Participants will be instructed to tell their Providers if they have participated in other research studies or received any other medical care involving radiation in the recent past.	Unlikely
Phlebotomy	Phlebotomy can cause pain, bruising at the site of the venipuncture, nerve damage, hematoma or infection	Rare
Electrical stimulator/weights (Risk of fracture)	SCI is commonly associated with bone weakness and weight bearing on the participant's limbs while exercising on the rowing machine may increase risk of fracture to already weakened bones.	Rare

Autonomic Dysreflexia (AD)	Weights and exercise to limbs of participants may pose as noxious stimuli that may lead to symptoms of AD (headache, pounding in the head, ringing in the ears, dizziness, blurry vision, sweating, anxiety, flushing, tightness in the chest, stuffy nose, heart flutters, or difficulty breathing), especially in those with cervical level of injury and high thoracic level of injury (T6 and above).	Rare
Falls	Falls could occur during training or transfer unto testing equipment (MRI/DXA table or in the home during transfer to/from wheelchair unto rowing machine.	Rare
Risk of Fracture	SCI is commonly accompanied by bone weakness and weight bearing on the participants' limbs may increase their risk of sustaining stress/low impact mechanical fracture.	

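### Session blood pressures and sessions suspended under the 20 mmHg rule have no by-arm summary, and whether a symptom-free rise is an adverse event rests on unmasked investigator opinion

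*Combined protocol and SAP*

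**What the plan says.** The risk table in Risk to Subjects names autonomic dysreflexia (AD) as a hazard of the training: "Weights and exercise to limbs of participants may pose as noxious stimuli that may lead to symptoms of AD". It rates the risk as rare and places it especially at cervical and high thoracic levels, T6 and above.

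The Blood Pressure (BP) Monitoring paragraph sets three readings per session. First, "The caregiver will measure the participant's BP before starting the exercise, record the reading and leave the BP cuff in place". Then, "About 15 to 20 minutes into the exercise, another BP reading will be taken and the final reading at the end of the exercise". The stated purpose is to guard against AD.

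Protection Against Risk, under autonomic dysreflexia, gives two triggers. One is symptoms: "established AD protocol followed should participant experience AD symptoms". The other is the reading itself: "Any significant rise in BP greater than 20 mmHg above resting BP, the intervention will be suspended immediately and AD protocol instituted". The second does not require a symptom.

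The Adverse Events section defines an adverse event as an experience "which, in the opinion of the investigators, was harmful to the research participant", or that increased the risk of harm, or that adversely affected the balance of risk and benefit. Vital signs are among the listed sources. Events go into the participant's file and an annual summary to the IRB.

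The Data Analysis Plan says of session data: "Means and SD will be estimated for utilization (number of sessions completed), with each outcome". It adds ANCOVA for each outcome. Statistical Analyses promises means, SDs, frequencies and percentages for study variables generally. Neither names session BP, AD, suspended sessions or adverse events by arm. The recruitment section includes safety in the primary goal.

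**The concern.** The protocol has an objective, repeatedly measured signal of a harm that it attributes to its own intervention, with a numerical trigger already attached. No provision carries that signal into a result. The only named route to a report is the adverse event definition, which depends on judgement. The PI assigns participants and supervises training by telehealth, so the judgement is made with knowledge of the arm.

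Two things are at stake. A symptom-free rise that suspends a session and then settles could be judged not to be an adverse event, and so appear in no comparison of the arms. Suspensions also reduce the training delivered, possibly more in one arm, and the utilization figure is not designed to show this. A later, larger trial would rely on this pilot for both.

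**Working it through.** **The plan's own calculation.** The only design figure is 80% power for d = 0.9 with 10 per group and alpha 0.25. Two-sided, the normal approximation gives 0.806 and the noncentral t (18 df) gives 0.796, so the figure reproduces. The point does not depend on it.

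**Volume of readings.** Inputs: two sessions a week in both arms (Home Video Telehealth Service), nine months, 20 participants (Subjects), three readings per session (BP Monitoring). Two assumptions: nine months is 36 to 39 weeks, and the BP paragraph applies to both arms (it follows the passive-movement section but is worded generally).

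- Sessions per participant: 36 × 2 = 72 to 39 × 2 = 78.
- Sessions in all: 72 × 20 = 1,440 to 78 × 20 = 1,560.
- Readings in all: 1,440 × 3 = 4,320 to 1,560 × 3 = 4,680.
- If every participant misses the 15% allowed in Subject's burden: 0.85 × 4,320 = 3,672 to 0.85 × 4,680 = 3,978.

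**Tracing one episode.** Take a symptom-free rise of more than 20 mmHg at the mid-session reading.

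1. *Recording.* The protocol expressly asks the caregiver to record the pre-exercise reading. It says of the later two only that they will be taken. No form or transfer to the study team is described.
2. *Management.* The session is suspended. No suspension record or reason field is described.
3. *Adverse event.* The episode qualifies if the investigators think it harmful, think it raised risk, or think it worsened the balance of risk and benefit. No BP threshold settles the matter.
4. *Oversight.* The annual IRB summary and the DSMB letter (Data and Safety Monitoring Plan) report adverse events, so they inherit step 3. Neither is said to be split by arm.
5. *Utilization.* The plan counts sessions completed and does not say how a suspended session is classed. If it counts as completed, utilization overstates training delivered. If it does not, it is pooled with sessions missed for illness or holidays. Either way the number of suspensions cannot be recovered.
6. *General summary.* Frequencies and percentages could accommodate a count of rises, but no such variable is defined. The assessment points are baseline, 4.5 and 9 months, not sessions.

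No step assures a by-arm count.

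**What a participant-level count can show.** With 0 of 10 participants affected in an arm, the exact one-sided 95% upper limit is 1 − 0.05^(1/10) = 0.259, or 25.9%. The two-sided 95% interval has upper limit 1 − 0.025^(1/10) = 0.308, or 30.8%. The table would be descriptive, and its intervals would keep a zero count from being read as proof of safety.

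**The case against.** The strongest reply is that the plan is not blind to these episodes. The adverse event definition has three parts, and a rise that stops a session could fit the second or third. Vital signs are a listed source, files are reviewed every ten days, and the PI stays on video until symptoms resolve. The DSMB letter covers study-related adverse events and adherence. The general summary promises frequencies and percentages as well as means. All of this stands. A reader might infer that an event counts only if judged harmful, or that symptom-free rises are bound to go unreported. The documents do not support either reading: they support that such rises could be missed, because each route passes through opinion or lacks a defined variable.

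It might also be inferred that rises could never be interpreted afterwards. That is wrong on injury level, which is established for everyone by neurological examination at screening. AD symptoms are also a separate trigger from the BP rise.

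A further objection is that a count on the 20 mmHg trigger needs definition, since the protocol does not say systolic or diastolic and does not define resting BP. This is correct, and the table must settle it for analysis purposes. So is the objection that 10 per arm cannot support a grid of arm, phase, level and symptoms, and that controls have no open-chain or rowing phase.

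**Conclusion.** The point holds as a reporting gap. Session BP readings and suspensions have no specified by-arm summary, and the adverse event status of a symptom-free rise rests on the opinion of investigators who supervise the sessions with no masking described. Under-reporting is possible, not certain.

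Its size is the volume of unassigned data: about 4,320 to 4,680 readings if every session takes place, or about 3,670 to 3,980 at the permitted 15% missed. This assumes 36 to 39 weeks and BP taken in both arms. The documents give no frequency of rises beyond calling AD rare, so neither the number of episodes lost nor any bias between arms can be estimated. The efficacy comparisons are not affected directly. This is an inexpensive improvement that should be made because safety is part of the stated primary goal. It raises no objection to the clinical rule or to how often BP is read.

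**What to change.** **Data capture.** Record all three readings of every session, and every suspension with its reason and any symptoms.

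**Data Analysis Plan.** Report by arm, whether or not an adverse event is declared:

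- (a) the number of participants with at least one session rise above the protocol's existing 20 mmHg trigger, measured against that session's pre-exercise reading, systolic and diastolic shown separately, with exact confidence intervals;
- (b) each participant's percentage of sessions with such a rise;
- (c) suspended sessions, counted separately from sessions completed.

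Show training phase (intervention arm only) and injury level (T6 and above, below T6) as descriptive listings only.

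**Adverse Events.** Keep the investigators' opinion on harm and on relation to the study as a separate field that does not decide whether an episode enters this table. There is no need to declare every suspension an adverse event.

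The pre-exercise reference and the systolic/diastolic split are definitions for the table only; the clinical management rule is unchanged. The cost is entry of session BP readings, including the two later ones that the protocol does not expressly ask to be written down, a suspension field, and one more descriptive table. No additional measurement is required.
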